4.3. Expected Benefits

The proposed research may result in direct benefits to participants and we expect that these benefits will outweigh the minor risk associated with participating in this research study. Individuals who complete the mindfulness training may experience reduced levels of distress, depression, and impulsivity; and an improved quality of life. Individuals who complete the general health intervention may improve their health behaviors. The magnitude of the benefits may be mild to moderate, and such benefits may last for the duration of the intervention and likely for the following months. Participants may also benefit from receiving additional medical assessments (e.g., sexually transmitted infection testing). By participating in the research, participants will also benefit from knowing they may ultimately be helping others to reduce their risk behavior, adhere better to their HIV treatments, and improve their health.

4.4. Data Safety and Monitoring Plan

Several different entities will safeguard the participants' safety and the integrity and quality of the data.

1. Institutional Review Board (IRB) at The Miriam Hospital: The study will be submitted for approval and meet all IRB requirements and directions.

2. PIs (Drs. [name] and [name]) will closely supervise all study activities on a day-to-day basis. They will meet weekly with the Project Director, [name] and other study personnel to monitor recruitment procedures, accrual and retention, side effects, and data integrity in order to take the necessary measures in a timely fashion.

3. Independent Monitoring Committee (IMC): Consistent with NIH guidelines for smaller studies (see: <http://nccam.nih.gov/grants/policies/data-safety-monitoring>) an IMC will be responsible for monitoring the safety of participants and the validity and integrity of the data. IMC members will include experts in HIV/AIDS, mindfulness, and statistics; members will be approved by the Program Officer of the NIH funding Institute (NCCIH). The IMC will meet yearly, either in person or via conference call. However, the IMC will convene on a more frequent (i.e., ad hoc) basis when immediate study concerns arise. At both scheduled and ad hoc meetings, they will review adverse events, re-evaluate measures for the protection of human subjects if needed, and re-assess the risk/benefit ratio of the study. A report will be compiled after each meeting and will include (a) a list of adverse and serious adverse events classified by severity and likelihood of being related to the study intervention; (b) whether adverse event rates are consistent with pre-study assumptions; (c) rates and reasons for study withdrawal; (d) whether all participants met entry criteria; (e) whether continuation of the study is justified. Summary reports of IMC meetings will be sent to the PI, the IRB and to the funding NIH agency and included in the annual NIH report (non-competing continuation grant) for the project.

Study safety and progress will be monitored according to the schedule outlined in the table below (and more frequently, if needed).

Table 1.	Frequency of data collection	Frequency of data review	
Data type	PD	PIs	IMC
Accrual, retention and attrition	Weekly	Every 2 weeks	Yearly
Adverse events *	Weekly	Weekly	Yearly
Participants' compliance to the intervention protocol	Weekly	Every 2 weeks	Yearly
Providers' compliance to intervention protocol	Weekly	Every 2 weeks	Yearly
Missing data/data integrity	Weekly	Every 2 weeks	Yearly

* Please note: serious adverse events will be reported within 24 hours to the IMC, IRB,

and to the sponsor (NIH) in accordance with their requirements.

4.5. Adverse Events and Serious Adverse Events

a. **Definition.** An adverse event (AE) is defined as any untoward medical occurrence in a participant temporally associated with participation in the clinical study. An adverse finding can include a sign, symptom, abnormal assessment (laboratory test value, vital signs, electrocardiogram finding, etc.) or any combination of these. A Serious Adverse Event (SAE) is any adverse event that results in one or more of the following outcomes:

- Death
- A life-threatening event
- Inpatient hospitalization or prolongation of existing hospitalization
- A persistent or significant disability/incapacity
- Important medical event based upon appropriate medical judgment

Note: A birth defect is a highly unlikely event considering our study intervention. This outcome has been excluded.

b. **Classification of AE Severity.** AEs will be labeled according to severity, which is based on their impact on the patient. An AE will be termed ‘mild’ if it does not have a major impact on the patient, ‘moderate’ if it causes the patient some minor inconvenience and ‘severe’ if it causes a substantial disruption to the patient’s wellbeing.

c. **AE Attribution Scale.** AEs will be categorized according to the likelihood that they are related to the study intervention. Specifically, they will be labeled either definitely, probably, possibly or unrelated to the study intervention. The determination of whether an AE is related to the study intervention will be made by the PD. If relatedness is unclear, the PD will seek the guidance of the PI.

Reportable and non-reportable events. The IRB at TMH requires reporting of all SAEs as well as of those AEs that are unanticipated and related to the study protocol or procedures (that is, they are “unlikely”, “possibly”, “probably” or “definitely” related). Unanticipated AEs are events, signs and symptoms that are not listed as risks on the consent form. Please note that AEs that are either anticipated or are “definitely not” related to the intervention procedures **are not reportable to the IRB at TMH.**

4.6. AE Reporting Procedures and Follow-Up

All *reportable AEs* (see 4.5. for definition) will be reported by the PIs to the Institutional Review Board (IRB) at TMH. Serious adverse events (SAEs) are reported to the IRB within 24 hours as described below (“SAE reporting”). All other reportable adverse events will be reported during the routine annual continuation reports to the IRB. In addition, all AEs (reportable and non-reportable) will be provided to the Chair of the IMC prior to each IMC meeting and to the NCCIH program officer, annually.

All intervention visits (mindfulness and control sessions) and follow-up assessments will include proactive assessments of potential adverse events. The PD will record all AEs and SAEs in a secure database using the format in the example below:

Subject Identifier	AE Onset	AE End	AE Code	Severity	SAE? (y/n)	Relatedness	Action Taken	Outcome	Comments	
Subj001	11/1/15			1		2	1	1	Subject felt anxious during MT; resolved within 15 minutes	
Subj002										
Subj003	12/18/15			3		0	4	4	Subject fell while hiking; broke leg; withdrew from study	
Severity of AE: 1 = Mild 2 = Moderate 3 = Severe 4 = Life threatening or disabling		Relatedness to intervention: 0 = Definitely unrelated 1 = Unlikely 2 = Possibly related 3 = Probably related 4 = Definitely related			Action Taken: 0 = None 1 = Intervention modification 2 = Medical intervention (specify in comments) 3 = Hospitalization 4 = Intervention discontinued 5 = Other (specify in comments)			Outcome: 1 = Resolved 2 = Recovered with minor sequelae 3 = Recovered with major sequelae 4 = Continuing treatment 5 = Condition worsening 6 = Subject death		

Participants will be asked about all AEs at each intervention session and at each follow up assessment. AEs will be recorded on the AE log. The PD will report all AEs to the PIs as soon as possible. All AEs will be assessed to determine their classification and whether they meet criteria for an SAE. The PD will refer participants to their own physician for assistance with adverse symptoms. Each week the PIs will review AE reports from the previous week for events that were reported as new or continuing, and will follow all AEs to the point of a satisfactory resolution. The PIs will be available at all times to discuss other adverse symptoms with the PD and the study participants.

SAE Reporting. SAEs that are unanticipated, serious, and/or possibly related to the study intervention will be reported to the IMC, the IRB at TMH, and to the sponsor (NIH) in accordance with their requirements.

- Unexpected fatal or life-threatening AEs related to the intervention will be reported to the NCCIH Program Officer within 7 days. Other serious and unexpected AEs related to the intervention will be reported to the Program Official within 15 days.
- Anticipated or unrelated SAEs will be handled in a less urgent manner but will be reported to the Independent Monitor(s), IRB, GCRC/CTSA, NCCIH, and other oversight

organizations in accordance with their requirements. In the annual AE summary, the Independent Monitor(s) Report will state that they have reviewed all AE reports.

Stopping rules. Considering the low-risk of this study, stopping rules have not been established. However, the IMC will closely monitor the risk/benefit ratio and the progress of the study and should issues in accrual, retention, data quality or safety arise, will take prompt action including considering the interruption of the study. Given the low risk of this study, no interim analyses are proposed.

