4.2. Protection Against Possible Risks

Possible risks during the study involve:

- a. Emotional discomfort during mindfulness practice
- b. Breach of confidentiality
- c. Minor side effects from venipuncture for assessments of viral load
- d. Depression and Suicidality

The level of risk for each of these events is minimal.

a. Emotional discomfort during mindfulness practice: Psychological distress during mindfulness practice is mild, of short duration, and rarely occurs in absence of ongoing serious psychiatric conditions; participants with suicidal ideation and ongoing psychosis will be excluded from participation in the study. In case a patient presents signs of severe psychological discomfort during or between sessions, he/she will be excused from participating in the mindfulness intervention. The mindfulness instructor will actively inquire at each phone session about psychological side effects that might occur during the session or during individual practice. Mindfulness instructors are experienced and trained on how to help individuals

presenting such issues. Participants will also be instructed to contact the Project Director (PD) should any discomfort arise during the training.

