6.3. Retention Plan

Patients will be asked to provide two different telephone numbers (home and mobile phone number) and an email address. Participants will be asked to provide contact information for two locators to be used in the event that contact is lost with the participant. Locators will not be given information about the nature of the research study. The study tracking system will identify participants due for a visit. We will send mail/email reminders or phone messages to remind patients of their follow-up appointments. Participants who wish to drop out of the study will be queried as to their reasons for doing so and every attempt will be made to address their concerns. In addition, we will provide monetary compensation to patients for their time and expenses. Participants will receive \$40 cash for the baseline assessment, \$40 cash for the post-intervention assessment, \$50 cash for the follow-up assessment and \$10 cash each for the pill count telephone calls (seven total) for a total of \$200.

If a participant does not complete all of the baseline procedures (including the two pill counts) within 60 days of enrollment, then he or she will be considered lost to follow-up.

If a participant does not complete two intervention weeks in a row he or she may be withdrawn from the intervention portion of the study per PD and PI discretion. These participants would still be contacted for pill count assessments and follow-up assessments.

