"A pill counter will call you several times during the study to talk to you for the study. The call will be done on the phone while you are home. On the phone calls, the pill counter will ask you to count your medications and tell her how many you have received and what you have left. It is very important we receive accurate information."

Prior to beginning the practice pill count, review the sample pharmacy label with the patient. With the Consultant's assistance, the TMH pill counter will highlight the pertinent information that will be used each month.

Run through a practice pill count using the pills that have been brought in for the baseline assessment.

BE SURE TO EMPHASIZE THE IMPORTANCE OF HAVING ALL MEDICATIONS OUT FOR THE PHONE CALL.

The Pill Counter will run through 3 sample question to demonstrate each type of response. Mention that the caller will also ask some questions about how the participant has been feeling and related issues.

Phone Assessment Training

1. Review the reason for the medication assessment: to learn how people are using their medications so that we can develop better health programs.
2. Provide Health and Assessment Kit.

Contents:

The Pill Tray
Pill Knife
Hand Wipes

3. Explain the pill count protocol. Use the Pill Counting Demo Kit to demonstrate how to count pills.

Mindfulness Training for PLWH

4. Practice a pill count with the Interviewer present. Pour the pills onto the pill tray. Instruct the participant to count their pills out loud by using the pill knife and sliding the pills into the valley of the pill tray. After all of the pills are counted have the participant put the pills back in the medication bottle and count the pills a second time. If the participant does not have medications to count, use the candy (Skittle, Tic Tacs, etc.).
5. Review protocol – answer questions – trouble shoot – problem solve

The Intake Interview is completed....participant given...

Copy of consent form
Take Home Kit
Incentive Payment

Phone Assessments and Pill Count

Time 0 Phone Assessment

Ideally participants are called within 3 days of Initial Intake for their Time 0 phone call.

Materials Needed for Phone Assessments

Previous Call Information Sheet

Assessment Form

Phone Tracking Sheet-(log of participants contacted with their participant ID)

Timing of interviews

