- appears severely distressed during any in-person session (i.e., screening, baseline, or follow-up; as determined by recruiter judgment), or
- reports suicidal thoughts at any time to PD or Instructor, initiate a “distress check” to assess suicidality. This check must be conducted in a sensitive and caring way. For example, you can say to the participant the following: *“I would like to check in with you about how this experience was for you. I asked a lot of questions, and want to check in to ask how are you doing?”*

If participant says he/she is okay and does not meet any of the above criteria for enacting the suicide safety protocol, no further intervention will be taken.

However, if participant says she/he is upset, then the PD or Instructor will say: *“It is not uncommon for people to feel upset or emotional after answering questions like this (or, talking about experiences like this). We do ask many personal questions. It is also not uncommon for people to have thoughts of hurting themselves. Have you had thoughts of actually hurting yourself?”*

If participant has not had any thoughts of hurting herself and does not meet any of the criteria above for enacting the suicide safety protocol, then we will remind patients of the resources available for counseling within the Immunology Center. We will also give everyone a list of local agencies that provide counseling services, and say: *“You may find it helpful to contact one of these agencies to set up an appointment to talk to someone about the feelings that were raised today. Also, if you are ever in crisis or need to talk to someone immediately, you can call the Immunology Center.”*

If participant has had thoughts of hurting herself or meets any of the above criteria for enacting the suicide safety protocol, then we will start suicide safety protocol, described next.

Script to Screen for Suicidal Concerns

If suicidal thoughts or severe distress are reported at screening or during any intervention or assessment session, the PD or Instructor will start the suicide safety protocol.

The PD and Instructors will be trained to use the following script. If indicated (as outlined earlier), they will ask:

“I’d like to ask you a few additional questions, because I am concerned for your well-being and safety.

1. Have you ever attempted to harm yourself in the past?	NO	YES
2. Have you thought about how you might actually hurt yourself?	NO	YES → [How? _____]

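### No adverse-event question is specified for the 8 to 14 weeks between the post-intervention visit and follow-up, although monthly pill-count calls continue throughout

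*Combined protocol and SAP*

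**What the plan says.** Section 4.6 states the rule for soliciting AEs twice: "All intervention visits (mindfulness and control sessions) and follow-up assessments will include proactive assessments of potential adverse events", and later "Participants will be asked about all AEs at each intervention session and at each follow up assessment". No section places an AE question at any other contact.

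Table 1 in section 4.4 has the row "Adverse events * Weekly Weekly Yearly": weekly data collection by the PD, weekly review by the PIs, and yearly review by the Independent Monitoring Committee (IMC).

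Two provisions take people out of sessions. Under section 4.2(a), a participant with severe psychological discomfort is removed: "he/she will be excused from participating in the mindfulness intervention". Under section 6.3, someone who misses two consecutive weeks may be withdrawn from the intervention, but "These participants would still be contacted for pill count assessments and follow-up assessments".

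The pill-count calls are monthly (section 5.2) and seven are paid for (section 6.3). Appendix 3 tells staff, at the training visit: "Mention that the caller will also ask some questions about how the participant has been feeling and related issues". It also has the caller establish the dates of any hospital stay, for use in the adherence calculation.

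**The concern.** After session 8 the schedule contains no weekly contact. Read literally, section 4.6 leaves the interval between the last two visits without any AE question, and removes the weekly question from anyone who stops sessions early. The study still phones these people about once a month.

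The hospital item shows the practical consequence. Inpatient hospitalization is a serious AE under section 4.5, and section 4.6 sends serious AEs to the IRB within 24 hours. A caller who follows the reproduced Appendix 3 text exactly could learn of an admission, use its dates for the pill arithmetic, and have no instruction to report it.

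This matters more than usual because section 4.6 sets no stopping rules and plans no interim analyses. Under section 4.4 the IMC judges whether continuation is justified from AE lists and rates, so the completeness of those lists is its main safety input.

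**Working it through.** The plan states no figure for the interval between AE questions, so there is none to reproduce. The intervals follow from the stated windows.

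**Inputs**
- Eight weekly sessions (section 7.3). Put session *k* at week *k* − 1, so session 8 is at week 7.
- Post-intervention visit: 0 to 2 weeks after the final session (Table 8.1).
- Follow-up: 12 ± 2 weeks, that is 10 to 14 weeks, after the final session (Table 8.1).
- Pill-count calls: every 28 ± 7 days, with 14 to 42 days tolerated (Appendix 3).

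**Gap for everyone, post-intervention to follow-up**
- Shortest: 10 − 2 = 8 weeks. Longest: 14 − 0 = 14 weeks.
- With follow-up at exactly 12 weeks: 12 − 2 = 10 to 12 − 0 = 12 weeks.
- Section 3 times the two visits at 3 and 5 months from baseline, which differs from Table 8.1. On that timing the gap is 2 × 30.4375 / 7 ≈ 8.7 weeks, still inside the range.

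**Extra gap for early leavers, last attended session *k* to post-intervention**

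If the visit is tied to the planned session 8, the gap is (8 − *k*) + 0 to (8 − *k*) + 2 weeks.

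| Last session attended | Weeks to post-intervention visit |
|---|---|
| 1 | 7–9 |
| 2 | 6–8 |
| 3 | 5–7 |
| 4 | 4–6 |
| 5 | 3–5 |
| 6 | 2–4 |
| 7 | 1–3 |

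If the visit is tied to the person's own last session, this gap is 0 to 2 weeks. The protocol does not say which applies. Either way the 8 to 14 weeks follow.

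**Calls inside the common gap**
- 8 × 7 / 28 = 2.0 calls, up to 14 × 7 / 28 = 3.5 calls.

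**Longest planned gap with an AE question on each call**
- Target window: 35 / 7 = 5 weeks. Outer limit: 42 / 7 = 6 weeks.

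**Check on the number of calls**
- The payments in section 6.3 agree with seven calls: 40 + 40 + 50 + 7 × 10 = 200. Two of the seven fall at baseline, leaving five. From session 1 to a follow-up at week 7 + 12 = 19 there is room for 19 × 7 / 28 = 4.75 calls, so five roughly cover the period when sessions start promptly.

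**The case against.** The strongest reply is that the plan already has several safety nets. AEs are asked about at every session, and the log has an action code for stopping the intervention. The PIs review new and continuing events weekly and follow each to resolution (section 4.6). Participants who want to drop out are asked why (section 6.3). Participants are told to contact the PD about discomfort during training (section 4.2), and depression is scored at each data collection point. This is a 50-person, low-risk behavioural pilot, and the longest gap falls when no sessions are being delivered.

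Much of this stands, and it rules out several stronger readings:

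- **Selective under-counting.** A reader might infer that harm is missed precisely in those who stop because of it. The documents do not support that: the distress that ends sessions should already be a recorded AE under weekly review. Nor do they show that harm is likeliest after leaving.
- **No AE item on the calls.** The full monthly assessment booklet is not reproduced, so one can say only that no AE item is specified.
- **A flat contradiction with Table 1.** The table also enters weekly for accrual and missing data, so it may describe study-level monitoring rather than weekly questioning of each participant. The two sections need reconciling; neither is shown to be wrong.
- **Callers outside the suicide protocol.** One trigger in Appendix 5 is a participant who "reports suicidal thoughts at any time to PD or Instructor". Section 4.2(b) has assessors place the calls, but section 13.3 says the PD conducts all phone contacts, and Appendix 3 sends life-in-jeopardy cases to project management. This too is a matter for reconciliation.

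The safety nets do not reach new events that arise after the post-intervention visit, or after early exit, and are not volunteered. The instruction to contact the PD depends on the participant's initiative and concerns discomfort during training. Following recorded events to resolution does nothing for unrecorded ones.

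**Conclusion.** The point holds as a gap in planned ascertainment. No AE question is specified for any participant for 8 to 14 weeks between the post-intervention and follow-up visits. Early leavers have about 1 to 9 weeks more before that, or 0 to 2 weeks if their visit is counted from their own last session. Only new, unvolunteered events are exposed. No bias between arms has been shown or calculated.

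The figures assume weekly sessions without rescheduling. They also assume that the post-intervention visit counts as a follow-up assessment for AE purposes; section 8.4 groups the two visits, but section 4.6 does not define the term. If it does not count, completers wait 10 to 14 weeks from their last session. Early leavers would then wait from 1 + 10 = 11 weeks (leaving after session 7) to 7 + 14 = 21 weeks (leaving after session 1), with the visits tied to the planned session 8.

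This is an inexpensive improvement worth making, not a flaw that undermines the trial.

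**What to change.** 1. In section 4.6 and Appendix 3, add the same standard AE question to every pill-count call in both arms. Have the caller pass any event, including any hospital stay learned of, to the PD for the AE log the same day. The longest planned gap falls from 14 weeks to about 5 (6 at the outer limit), provided that calls are completed and continue until follow-up.
2. State in Table 1 what weekly AE collection means after session 8, so that it agrees with section 4.6.
3. Reconcile sections 4.2(b) and 13.3 on who places the calls, and reconcile Appendix 5 with the answer.

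The calls are already scheduled and paid for. The cost is a minute or two per call, a somewhat higher recorded AE count, and a chance that an answer reveals the arm to the person measuring adherence. That last risk arises if assessors place the calls, since section 7.6 does not say whether they are blinded; the PD is already unblinded. Asking after the pill count is complete, in neutral wording, limits it.
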